9.1 Adverse Events

9.1.1 Definition of Adverse Event

An AE is defined as any untoward medical occurrence in a subject while participating in a study that does not necessarily have a causal relationship with sipuleucel-T. An AE can, therefore, be any unfavorable and unintended sign (e.g., abnormal laboratory finding), symptom, or

disease temporally associated with sipuleucel-T, whether or not considered related to sipuleucel-T. AEs include exacerbation of a pre-existing illness, an increase in frequency or intensity of a pre-existing episodic event or condition, a condition detected or diagnosed after product administration (even though it may have been present prior to the start of the study) or a continuous persistent disease or symptoms present at Screening that worsen following the start of the study.

9.1.2 Categories for Ranking Severity of Adverse Events

The most current version of the National Cancer Institute Common Terminology Criteria for Adverse Events (NCI CTCAE) will be used to score AE severity by grades. In general, the following severity definitions apply:

Mild (grade 1):	The AE results in mild, easily tolerated symptoms, or is asymptomatic with clinical or diagnostic observations only. Intervention is not usually indicated.
Moderate (grade 2):	The AE produces moderate symptoms with discomfort sufficient to interfere with some aspect of the subject's normal daily activity. Minimal, local, or noninvasive intervention is required.
Severe (grade 3):	The AE is medically significant but not immediately life threatening, results in discomfort or disability which is incapacitating and prevents most normal daily activities, clearly damaging to the health, requiring hospitalization, prolongation of existing hospitalization or complicated treatment.
Life-threatening (grade 4):	The AE could reasonably be expected to result in death unless immediate medical intervention is undertaken.
Fatal (grade 5):	The AE results in death.

9.1.3 Relationship of Adverse Events to Sipuleucel-T

The following categories will be used to determine relationship of AEs to sipuleucel-T:

None:	The AE is clearly related to other factors, such as the subject’s clinical state, environmental factors, or other modes of therapy or concomitant medications administered to the subject.
Possible:	The AE follows a reasonable temporal sequence from administration of sipuleucel-T, but could readily have been produced by the subject’s clinical state, environmental factors, or other modes of therapy or concomitant medications administered to the subject.
Probable:	The AE follows a reasonable temporal sequence from administration of sipuleucel-T and could not readily have been produced by the subject’s clinical state, environmental factors, or other modes of therapy or concomitant medications administered to the subject.

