6.3 Discontinuation from Study

A subject may discontinue participation in the trial at any time without prejudice. If a subject withdraws consent for any further study involvement, complete withdrawal of consent must be documented in the subject's medical record. The date and reason for withdrawal will be recorded in the subject's medical record and on the eCRF.

Whenever possible, every subject who withdraws consent and discontinues from the study will undergo an Early Withdrawal Visit within 30 days following discontinuation notice. Subjects are encouraged to have, as standard of care, a systematic prostate biopsy (≥ 10 cores) with or without MRI at the investigator's discretion prior to study withdrawal. The H&E and special-stained slides from this biopsy will be submitted for BICR determination of their ISUP Grade Group classification prior to study withdrawal. All AEs considered by the investigator to be related to sipuleucel-T that are ongoing at the time of discontinuation will be followed by the investigator until resolution, return to baseline, or a determination by the investigator that no further improvement is expected. The investigator should make every reasonable attempt to ensure that the subject is contacted (via telephone or during the Early Withdrawal Visit) to obtain the final status of any AEs and concomitant medications.

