9.1.4 Recording and Reporting Adverse Events

All AEs and SAEs in the sipuleucel-T arm and control arm will be collected from randomization through the subject’s last study visit. AEs and SAEs will be reported and recorded in the subject’s medical record and entered on their eCRF.

All AEs and SAEs reported in either the sipuleucel-T or control arms will be followed by the investigator until resolution, return to baseline, or the investigator determines that no further improvement is expected until study completion. The start and stop dates, description, seriousness, toxicity, relationship to study treatment, and outcome will be recorded.

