8.2 Leukapheresis Variables

Number of Leukapheresis Received

Count of leukapheresis received is captured on the Leukapheresis Form at the scheduled 3 visits and unscheduled visits.

Central Venous Catheter (CVC) use

CVC use is defined as occurrence captured on the Central Venous Catheter Summary Form at any visit.

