12.7 Safety Analyses

12.7.1 Adverse Events

A summary of AEs, including the number and percentage of events reported, and the number and percentage of subjects

- reporting at least one AE,
- with at least one grade ≥ 3 AE,
- with at least one SAE,
- with at least one study drug related AE (probable or possibly related),
- with an AE leading to death

will be presented by study treatment arm in the Safety population. In the summary by worst National Cancer Institute Common Terminology Criteria for Adverse Events (NCI CTCAE) v5.0 grade, the AE with the highest or most severe grade will be counted when subjects have multiple AEs in a SOC or PT.

A breakdown of the number and percentage of subjects reporting each kind of AE above, categorized by SOC and PT, will be also presented. This breakdown will be sorted by PT within SOC. Note that counting will be by subject and not by event and subjects are only counted once within each SOC or PT. This breakdown will be repeated and sorted by descending frequency of PTs in the sipuleucel-T arm for subjects reporting at least one AE and subjects reporting at least one grade ≥ 3 AE. This breakdown will also be

repeated by worst CTCAE grade for subjects reporting at least one AE and subjects reporting at least one grade ≥ 3 AE, sorted by PT within SOC.

AEs occurred within 1 day after any leukapheresis will be summarized. Similarly, AEs occurred within 1 day after any infusion will be summarized.

Listings of AEs will also be presented.

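### The related-AE count leaves out AEs due to leukapheresis or a central venous catheter, because causality is graded only against administration of sipuleucel-T

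*Protocol*

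**What the plan says.** Protocol Section 9.1.3 introduces its scale with "The following categories will be used to determine relationship of AEs to sipuleucel-T" and has three grades:

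- *None*: "The AE is clearly related to other factors", with examples that name neither leukapheresis nor a catheter.
- *Possible*: "The AE follows a reasonable temporal sequence from administration of sipuleucel-T, but could readily have been produced by the subject’s clinical state", or by other listed factors.
- *Probable*: "The AE follows a reasonable temporal sequence from administration of sipuleucel-T and could not readily have been produced by" those same factors.

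Protocol Section 9.1.4 uses another term for what is recorded on each AE: "The start and stop dates, description, seriousness, toxicity, relationship to study treatment, and outcome will be recorded". The SAP uses a third. One row of the AE summary in Section 12.7.1 counts subjects "with at least one study drug related AE (probable or possibly related".

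Leukapheresis is part of every dose: Protocol Section 7.2.4 uses the cells from one procedure to make one dose. The control schedule (Protocol Table 2) contains none. A catheter is treated as something that some men have: "CVC use is defined as occurrence captured on the Central Venous Catheter Summary Form at any visit" (SAP Section 8.2). SAP Section 12.4.1 counts those men.

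On follow-up after withdrawal, Protocol Section 6.3 says: "All AEs considered by the investigator to be related to sipuleucel-T that are ongoing at the time of discontinuation will be followed by the investigator". Section 9.1.4 applies follow-up to all AEs in both arms.

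**The concern.** A man assigned to sipuleucel-T accepts the leukaphereses, and a catheter if he needs one, as well as the infusions. A man on surveillance accepts neither. An AE caused by collecting the cells would not have happened without assignment to sipuleucel-T, yet the scale asks only whether the infused product caused it.

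A reader of the study report is likely to take the related-AE row as the harm attributed to the treatment as a whole. If it covers only the infused product, it answers a narrower question than its label suggests. Because three terms are in use, two sites could also grade the same event differently.

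**Working it through.** The documents state no related-AE rate and no rate of leukapheresis or catheter events, so there is no planned figure to reproduce. The check is one timing calculation and a comparison of the text.

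**Timing.** Leukaphereses are about 2 weeks apart (Protocol Section 7.2.1), and each infusion follows about 3 days later (Section 7.2.5). With leukapheresis 1 on day 0:

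- leukapheresis k falls on day 14 × (k − 1): days 0, 14 and 28;
- infusion k falls on day 14 × (k − 1) + 3: days 3, 17 and 31;
- the gap from an infusion to the next leukapheresis is 14 − 3 = 11 days.

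**Grade that the text allows**

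| AE | Follows an administration? | Grade | In related row? |
|---|---|---|---|
| Between leukapheresis 1 and infusion 1 | No | *None*, by elimination | No |
| After infusion 1, clearly due to leukapheresis or catheter | Yes | *None*, since the cause is clear | No |
| After infusion 1, cause uncertain | Yes | *Possible* is open | Yes, if so graded |

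The first row is certain on the wording. The second follows from the definition of *None*. The third shows that *None* is not forced on every procedure-related AE.

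**Terms.** The Protocol grades against sipuleucel-T (9.1.3) and records against study treatment (9.1.4); the SAP counts against study drug (12.7.1). Protocol Section 7.2, headed as treatment, contains the leukapheresis subsections, which favours a broad reading of study treatment. SAP Section 9.3 equates a dose of study treatment in this arm with at least part of the first infusion, which favours a narrow one.

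**Population.** Take a man who has leukapheresis 1, suffers an AE and is never infused.

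- Protocol Section 10.2 includes him if leukapheresis counts as starting the treatment process.
- SAP Section 8.4.1 summarises AEs in this arm from the first leukapheresis onward, which covers his AE.
- SAP Section 9.3 excludes him, because it requires at least part of the first infusion. The AE tables of Section 12.7.1 use that set, so he is missing from the all-cause tables and the 1-day table too.
- SAP Section 12.4.1 still counts his leukapheresis, because exposure is summarised in the ITT set.

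SAP Section 12.6.1.3 reports that three men in this arm were replaced. Such men received no sipuleucel-T and are outside the safety set. The documents do not say whether any of them had a leukapheresis.

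**Size.** Planned exposure is 300 × 3 = 900 leukaphereses if every man completes the course. The actual number may be lower (Section 6.3.1 allows discontinuation) or higher (Section 7.2.6 allows repeats). Let p be the proportion of the 300 men with an AE of this kind and no other AE graded *Possible* or *Probable*. The row is then short by 300 × p men, or 300 × 0.01 = 3 men for each 1%. The documents give nothing from which to estimate p.

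**The case against.** The case against has real weight. The safety endpoint is the incidence of AEs in each arm, whatever their cause (Protocol Section 4.2, SAP Section 7.2.2). Four of the five subject-level rows in SAP Section 12.7.1 (any AE, grade 3 or higher, SAE, AE leading to death) take no account of causality. Control men have no leukapheresis, so the between-arm difference in those rows already includes procedure and catheter harm, without relying on open-label judgement of cause. AEs are summarised from the first leukapheresis, those within 1 day after any leukapheresis have their own summary, and catheter use is tabulated. All of this stands for men who are infused. What remains is that the 1-day summary assigns no cause, a later catheter event is not singled out, and no catheter-AE table is described.

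Study treatment can also be read to include leukapheresis, and no passage instructs sites to grade such events *None*. That is fair, but it leaves the count dependent on how each site reads an undefined term.

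On follow-up, Section 6.3 also asks for every reasonable attempt to learn the final status of any AE, so the tension with Section 9.1.4 is one of wording.

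The AE case report form and the table shells are not among the documents. A procedure attribution may already be collected.

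A reader might infer three stronger things. None is supported:

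- *That these harms disappear from the safety report.* For infused men they leave only the related count.
- *That the benefit-risk conclusion is therefore too favourable.* Nothing in either document makes the related row the basis of that conclusion.
- *That every dose needs a catheter.* The SAP records catheter use only as an occurrence.

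**Conclusion.** The point holds for the related-AE count. As written, AEs between leukapheresis 1 and infusion 1, and later AEs clearly due to leukapheresis or to a catheter where one is used, are graded *None* and left out of that row. They are also left out of its breakdown by system organ class and preferred term. AEs of uncertain cause after infusion 1 may still be counted.

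The direction is toward understatement; the amount cannot be computed. The conclusion assumes that sites apply the Section 9.1.3 wording literally and that the case report form carries no separate procedure attribution.

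The safety-set conflict is narrower in the men it affects but wider in effect: a man with leukapheresis and no infusion is absent from all the AE tables of SAP Section 12.7.1. The efficacy analysis is untouched. This is a low-cost improvement to safety reporting.

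**What to change.** 1. Use one defined term for causality in Protocol Sections 9.1.3 and 9.1.4 and SAP Section 12.7.1.
2. Add a second attribution item to Section 9.1.3 and the AE case report form: relationship to leukapheresis or central venous catheter, with the same three levels. Say which item the expedited-reporting trigger in Section 9.2.4 refers to, since it now names sipuleucel-T only.
3. In SAP Section 12.7.1 report three rows: related to sipuleucel-T, related to leukapheresis or catheter, and related to either.
4. Reconcile the safety set in SAP Section 9.3 with Protocol Section 10.2 and SAP Section 8.4.1, so that men who had leukapheresis but no infusion appear in these tables. Without this step the new rows miss the clearest case.
5. Reconcile the AE follow-up wording in Protocol Section 6.3 with Section 9.1.4.

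The cost is one case-report-form item, two extra table rows and some wording, with no new visits or procedures. The SAP already reports replaced subjects, so the item would have to be completed retrospectively for AEs already on file. The reported related-AE rate may be slightly less favourable.

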9.1.4 Recording and Reporting Adverse Events

All AEs and SAEs in the sipuleucel-T arm and control arm will be collected from randomization through the subject’s last study visit. AEs and SAEs will be reported and recorded in the subject’s medical record and entered on their eCRF.

All AEs and SAEs reported in either the sipuleucel-T or control arms will be followed by the investigator until resolution, return to baseline, or the investigator determines that no further improvement is expected until study completion. The start and stop dates, description, seriousness, toxicity, relationship to study treatment, and outcome will be recorded.

9.2 Serious Adverse Events

9.2.1 Definition of Serious Adverse Event

An SAE is defined as any adverse drug experience occurring at any dose that results in any of the following outcomes: death, a life-threatening adverse drug experience, subject hospitalization or prolongation of an existing hospitalization, a persistent or significant disability/incapacity, or a congenital anomaly/birth defect. An important medical event that may not result in death, be life-threatening, or require hospitalization may be considered an SAE when, based upon appropriate medical judgment, it may jeopardize the subject and may require medical or surgical intervention to prevent one of the outcomes listed in this definition. Examples of such medical events include allergic bronchospasm requiring intensive treatment in an emergency room or at home, blood dyscrasias or convulsions that do not result in subject hospitalization, or the development of drug dependency or drug abuse.

9.2.2 Recording and Reporting of Serious Adverse Events

All SAEs in the sipuleucel-T arm and control arm from randomization through the subject's last study visit will be reported on sponsor's SAE Report Form.

All SAEs reported in both arms will be followed by the investigator until resolution, return to baseline, or the investigator determines that no further improvement is expected until study completion.

SAEs must be reported to sponsor or designee within 24 hours of the clinical trial site's awareness of the events by completing the sponsor's SAE Report Form if they meet the criteria described in [Section 9.2.1](#). If access to the SAE Report Form is unavailable for any reason, the SAE information must be reported to sponsor or designee within 24 hours by email or facsimile and a completed written report using sponsor's SAE Report form within 3 business days to:

Dendreon Pharmaceuticals LLC

Attention: [contact]

Significant new information regarding each SAE must be reported to sponsor or designee by recording the information on the SAE Report Form within 24 hours of the clinical trial site's awareness of the new information and reported as noted above.

9.2.3 Death Reports

Deaths that occur during the study will be reported as SAEs and will be recorded in the subject's medical record, sponsor's SAE Report Form and on the eCRF.

9.2.4 Expedited Reporting Requirements

Sponsor will notify the appropriate regulatory authorities and all participating Principal Investigators of any AE that is serious, unexpected and considered to be at least possibly related to sipuleucel-T. Such notification will be provided within 15 calendar days after Sponsor or designee's initial receipt of the information. If such an event is fatal or life-threatening, the appropriate regulatory authorities will be notified no later than 7 calendar days after Sponsor or designee's initial receipt of the information.

Serious adverse events that are expected, such as disease progression, will not be reported by sponsor on an expedited basis. See the sipuleucel-T Investigator's Brochure for additional information regarding expected SAEs.

The Principal Investigator is responsible for notifying the relevant IRB of any SAE that occurs in a subject participating at their clinical trial site or any IND Safety Reports issued by sponsor, unless otherwise instructed by relevant IRB policy.

9.3 Laboratory Test Result Abnormalities

The following laboratory abnormalities will be considered AEs and recorded in the subject's medical record and on the eCRF:

- Any clinically significant result that is not part of another reported clinical diagnosis
- Any result that meets the definition of an SAE
- Any result leading to discontinuation or interruption of sipuleucel-T
- Any result that requires therapeutic intervention or a change in subject management

Laboratory abnormalities that do not meet the above conditions will not be recorded on the eCRF.

10.0 STATISTICAL CONSIDERATIONS

The Phase 3, open-label study is designed to assess the effects of sipuleucel-T in subjects on AS. Subjects will be randomized 2:1 to either a sipuleucel-T arm (investigational arm) or a control arm, stratified by the ISUP Grade Group 1 or 2 and the number of biopsies showing the presence of disease prior to registration. Data will be analyzed by arm under the intent-to-treat (ITT) principle. Generally statistical tests will be performed at the 2-sided 0.05 significance level unless otherwise noted.

The phrases 'statistical analysis' or 'analysis' will be used to mean inferential analysis (such as performing tests of significance, reporting p-values and confidence intervals). When no inferential analysis will be performed, the phrases 'descriptive analysis' or 'descriptive statistics' will be used (for instance, producing summary tables of means, standard deviations, percentages of responders).

Statistical analysis will be done by the sponsor or under the authority of the sponsor. A general description of the statistical methods to be used to analyze the efficacy and safety data is outlined below. Details will be provided in the Statistical Analysis Plan (SAP).

10.1 Sample Size Considerations

The primary endpoint will analyze approximately 450 subjects randomized (2:1 sipuleucel-T versus control arm), and for each subject, is dichotomous with success defined as having been observed to be free of histopathologic upgrade after 36 months of follow-up. Based on data available, it is estimated that the proportion of histopathologic upgrading by 36 months following randomization for control arm subjects will be approximately 0.30. While there is no prior information on treatment response to sipuleucel-T in early stage disease available, a meaningful hypothesized reduction in this proportion is a reduction by 0.14, giving a projected outcome proportion of upgrading in the sipuleucel-T arm of 0.16. The null hypothesis of both arms having a proportion of 0.70 (= 1- 0.3) being free from upgrading at 36 months versus the

specific alternative hypothesis of a sipuleucel-T arm outcome of 0.84 (= 1- 0.16). The odds ratio associated with the specific alternative hypothesis is 2.25 (sipuleucel-T arm odds over control arm odds). Based on an overall 1-sided alpha of 0.025 approximately 300 subjects in the sipuleucel-T arm and 150 subjects in the control arm will provide 90% power to demonstrate the superiority of sipuleucel-T to control.

10.2 Analysis Populations

The Safety Analysis Population is defined as all randomized patients; the Sipuleucel-T safety population must have begun the treatment process.

The intent-to-treat (ITT) population is defined as all randomized subjects.

The Per Protocol (PP) population is defined as the subset of patients in the ITT population who have completed all assessment per the protocol.

10.3 Efficacy Analysis

The phrases ‘statistical analysis’ or ‘analysis’ will be used to mean inferential analysis (such as performing tests of significance, reporting p-values and confidence intervals). When no inferential analysis will be performed, the phrases ‘descriptive analysis’ or ‘descriptive statistics’ will be used (for instance, producing summary tables of means, standard deviations, percentages of responders). All efficacy analyses will be conducted on the ITT population and the per protocol population.

Unless otherwise specified, the statistical tests are based on the superiority hypothesis using a one-sided p-value of 0.025 (equivalent to two-sided 0.05 with a result in the hypothesized direction). The final analysis will be performed after all subjects have completed the 36 month biopsy, or have histopathologic upgrade or have withdrawn from the study.

